11.3 Analysis of Primary Endpoint

The study is based on the primary endpoints for effectiveness and interval estimates of the safety of the device. The study will be considered a success from a statistical standpoint if:

- 1. Both primary analysis variables pass their respective hypotheses, i.e., H_{a0} and H_{b0} below are rejected in favor of H_{a1} and H_{b1}, respectively,
- 2. The rate of pre-specified adverse events per dialysis interval is estimated to be within the specified error of estimation for each treatment period.

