11.6 Analysis of Adverse Events

All study-emergent AEs occurring during the study sessions will be recorded and classified on the basis of MedDRA terminology for the ITT population. Study-emergent AEs are those AEs with an onset on or after the date of first study treatment. All study-emergent AEs will be categorized by study period (In-Center or In-Home), the number of Subjects reporting study-emergent AEs, severity, device relationship, and seriousness. Serious adverse events (SAEs) will be listed by Subject. SAEs will be categorized by study period, severity, and device relationship. Each Subject will be counted only once within a category using the event with the greatest device relationship and greatest severity.

For each treatment period, a 95% confidence interval will be computed on the pre-specified adverse event rate per dialysis interval. This confidence interval will be computed using the Least Square Mean for the respective treatment period from a generalized linear model containing terms for Subject, arm and time points (i.e., a repeated measures analysis using GEE) using a Poisson link function and AR(1) covariance structure.

Summary statistics (mean, sample size, standard deviation, minimum, maximum, median) will be computed on the number of pre-specified adverse events per dialysis interval for each treatment period. The same summary statistics will be calculated by treatment period for the rate of pre-specified adverse events per 100 dialysis treatments.

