1.3 Sample Size

The sample size for the study is based on the primary effectiveness endpoint, weekly standardized Kt/V and the primary safety endpoint, the number of pre-specified, serious, device related, treatment emergent adverse events during a dialysis interval.

A hypothesis test that the treatment period mean weekly standardized Kt/V is statistically significantly greater than 2.1 will be carried out for both the In-Center and In-Home treatment periods. Given that the true treatment period mean Kt/V is 2.5 units, with one-sided $\alpha=0.025$, a sample size of $n=11$ subjects, each measured weekly for at least 8 weeks of treatment, will have >90% power to detect that the mean is statistically significantly greater than 2.1 in the treatment period. This sample size calculation assumed a standard deviation of 0.7 units,

based on Sands et al (2009)¹, and a within patient correlation of Kt/V values of $\rho=.50$. The sample size calculation was based on an asymptotic normal theory one sample test using variance estimates that included covariance terms for repeated (weekly) measurements on each patient with a block diagonal first order autoregressive (AR(1)) covariance structure.

For the safety endpoint, the needed sample size yields an estimate of the rate of pre-specified adverse events per 100 dialysis treatments in each treatment period (In-Center and In-Home use), to a margin of error of less than 1 event per 100 treatments. With a two-sided $\alpha=0.05$, in order to construct a 95% confidence interval on the rate of pre-specified adverse events per 100 dialysis treatments with half-width less than 1 event per 100 treatments, the sample size required would be $n=30$ subjects with 4 dialysis intervals per week for a minimum of 8 weeks (i.e., 30 subjects with a minimum of 32 treatments). The sample size calculation was based on an asymptotic normal theory one sample test using variance estimates that included covariance terms for repeated measurements (4 dialysis intervals per week for 8 weeks) on each patient with a block diagonal first order autoregressive (AR(1)) covariance structure. This sample size calculation assumed a standard deviation of 0.8 AEs per dialysis interval and a within patient correlation of pre-specified AE counts of $\rho=.50$.

Given the sample sizes necessary to satisfy the power requirements for the Kt/V endpoint and the composite safety endpoint, a sample size of $n=30$ subjects will be needed for the study.

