4.2 Analysis of Effectiveness Variables

4.2.1 Analysis of Primary Effectiveness Variable

The weekly standardized Kt/V values will be computed for each subject for the In-Center period and for the In-Home period. The following hypotheses will be tested at a one-sided $\alpha=0.025$ level of significance:

$$H_{a0}: \mu_{IC} \leq 2.1 \text{ vs. } H_{a1}: \mu_{IC} > 2.1$$

and

$$H_{b0}: \mu_{IH} \leq 2.1 \text{ vs. } H_{b1}: \mu_{IH} > 2.1$$

where μ_{IC} is the treatment period mean weekly standardized Kt/V value for the In-Center arm and μ_{IH} is the treatment period mean weekly standardized Kt/V value for the In-Home arm. These hypotheses will be tested using the Least

Square Mean for the respective treatment period from a repeated measures analysis of variance (RMANOVA) containing terms for subject, treatment arm (i.e., In-Center treatment period and In-Home treatment period), and time points (weeks) and using an AR(1) covariance structure.

Summary statistics (mean, sample size, standard deviation, minimum, maximum, and median) will be computed on the weekly standardized Kt/V values for each treatment period.

All analyses of the primary effectiveness variable will be performed on the ITT population with no missing value imputation, the ITT population with missing value imputation, and the PP population. The ITT population with no missing value imputation is the primary analysis set.

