5.2 Analysis of Safety Variables

The following describes the safety analyses to be performed for the study. Analysis of the primary safety variable will be performed on the ITT population. All other safety analyses will be performed on the safety population.

Pre-specified Adverse Events for Primary Safety Variable

For each treatment period, a 95% confidence interval will be computed on the pre-specified adverse event rate per dialysis interval. This confidence interval will be computed using the Least Square Mean for the respective treatment period from a generalized linear model containing terms for subject, treatment arm and time points (i.e., a repeated measures analysis using GEE) using a Poisson link function and AR(1) covariance structure. If the AE start date/time is missing, the AE will be counted in the interdialytic interval in which it was observed (if available) or will be randomly assigned (during the final data analysis for the study) to one of the interdialytic periods in the treatment period.

Summary statistics (mean, sample size, standard deviation, minimum, maximum, median) will be computed on the number of pre-specified adverse events per dialysis interval for each treatment period. The same summary

statistics will be calculated by treatment period for the rate of pre-specified adverse events per 100 dialysis treatments.

Additional Analyses of Pre-specified Adverse Events

A table will be provided to show the number and percentage of safety population subjects with at least one pre-specified AE by treatment period and overall for each dialysis treatment interval (treatment, interdialytic, pre-treatment).

A summary table will be constructed to display the following with respect to pre-specified AEs:

- Subjects with at least one pre-specified AE
- Maximum severity, per subject
- Highest relationship to device, per subject
- Highest relationship to treatment, per subject
- Subjects with at least one SAE
- Deaths

All Other Study-Emergent Adverse Events

A table will be provided to show the number and percentage of safety population subjects with at least one study-emergent AE by treatment period and overall for each dialysis treatment interval (treatment, interdialytic, pre-treatment). A similar table will also be provided to show the number and percentage of safety population subjects with at least one occurrence of an AE by categorization (pre-specified AEs or all other AEs) by treatment period and overall.

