^a Treatment number is relative to the given timepoint, where each week has 4 scheduled treatments.

^b URR is calculated as (Pre-Post BUN)/(Pre BUN).

STATKING Clinical Services (month day, year)

Source Program: xxxxxxxx.sas

Only selected time points and treatment numbers are shown on this mock table. The final table will display all time points (Weeks 2-9 for In-Center and Weeks 10-19 for In-Home) and all four treatment numbers within each time point.

Table 34. Summary Table of Clinically Significant Alarms
 Outset Medical - Study No. 2014-01
 ITT Population (N=xxx)

Alarm Type	Treatment Period ^a	
	In-Center	In-Home
Air in Venous Lines	xxx (xxx%)	xxx (xxx%)
Low Systolic Blood Pressure	xxx (xxx%)	xxx (xxx%)
High Venous Pressure	xxx (xxx%)	xxx (xxx%)
Low Venous Pressure	xxx (xxx%)	xxx (xxx%)
Blood Leak in Dialyzer	xxx (xxx%)	xxx (xxx%)
Alarms that End Treatment	xxx (xxx%)	xxx (xxx%)

^a Summaries per treatment period are the number and percentage of treatments with the respective alarm type. The denominator is the number of treatments for all ITT population subjects during the treatment period.
 STATKING Clinical Services (month day, year)
 Source Program: xxxxxxxx.sas

Table 35. Clinically Significant Alarms Summary Statistics
 Outset Medical - Study No. 2014-01
 ITT Population (N=xxx)

Alarm Type=xxxxxxxxxxxxxxxx

Treatment Period	Time Point	Treatment Number ^a	Mean	Std Dev	n	Min	Max	Median
N/A	Week 1	1	xxx	xxx	xxx	xxx	xxx	xxx
In-Center	Week 9	4	xxx	xxx	xxx	xxx	xxx	xxx
In-Home	Week 19	4	xxx	xxx	xxx	xxx	xxx	xxx

^a Treatment number is relative to the given timepoint, where each week has 4 scheduled treatments.
 STATKING Clinical Services (month day, year)
 Source Program: xxxxxxxx.sas

Only selected time points and treatment numbers are shown on this mock table. The final table will display all time points (Weeks 2-9 for In-Center and Weeks 10-19 for In-Home) and all four treatment numbers within each time point. The format of this table will be repeated for alarm type.

Table 40. Time to Resolve/Clear Alarms Summary Statistics
 Outset Medical - Study No. 2014-01
 ITT Population (N=xxx)

Treatment Period	Mean	Std Dev	n	Min	Max	Median
N/A	xxx	xxx	xxx	xxx	xxx	xxx
In-Center	xxx	xxx	xxx	xxx	xxx	xxx
In-Home	xxx	xxx	xxx	xxx	xxx	xxx

STATKING Clinical Services (month day, year)
 Source Program: xxxxxxxx.sas

Table 41. Prescription Changes Summary Statistics - Overall
 Outset Medical - Study No. 2014-01
 ITT Population (N=xxx)

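### The primary safety confidence interval rests on a period LS mean that, with a log link and class-coded time points, is a geometric average of rates and is not finite if a time point has no events

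*SAP*

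**What the plan says.** The primary safety variable (Protocol 5.2, SAP 5.1) is the mean count of pre-specified adverse events per dialysis interval. For its 95% interval, Protocol 11.6 states: "This confidence interval will be computed using the Least Square Mean for the respective treatment period". SAP 5.2 gives the same model, "containing terms for subject, treatment arm and time points", fitted by GEE "using a Poisson link function and AR(1) covariance structure". Neither section says what a time point is in this model, whether it is a class term, whether subject is a fixed effect as well as the cluster, or on what scale the LS mean is reported.

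The interval is tied to study success. The second criterion in Protocol 11.3 reads: "The rate of pre-specified adverse events per dialysis interval is estimated to be within the specified error of estimation for each treatment period". SAP 1.3 sets the target as an interval "with half-width less than 1 event per 100 treatments". Table 16 prints a mean beside this interval.

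For Kt/V, SAP 4.2.1 uses subject, treatment arm "and time points (weeks) and using an AR(1) covariance structure".

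**The concern.** A class-coded time term on the log scale changes what the period LS mean estimates. The LS mean averages the linear predictor over time points with equal weight. Back-transformed, this is the geometric mean of the time-point rates, which in a balanced design cannot exceed the arithmetic rate. If a time point has no event in either period, its coefficient runs to minus infinity and takes both period LS means to zero.

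Two things are at stake. The interval may describe a smaller quantity than the endpoint, so that Table 16 could show a raw mean beside an interval for something else. Also, a collapsed LS mean has a tiny back-transformed half-width, so the precision criterion could appear to be met because the fit failed.

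**Working it through.** **Inputs.** 30 subjects and 32 intervals per subject per period, so 960 intervals per period and 1,920 in both (SAP 1.3). Target half-width below 1 per 100, two-sided 0.05 (SAP 1.3). Event rates are assumptions, because the documents give none. A log link is assumed, because Poisson names a distribution and not a link.

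**The plan's own figure.** SAP 1.3 says: "This sample size calculation assumed a standard deviation of 0.8 AEs per dialysis interval", with correlation 0.5. Under AR(1) over 32 intervals, the variance of a subject mean is 0.8² × [32 + 2·Σ(32−k)·0.5^k] / 32² = 0.64 × 92 / 1024 = 0.0575. The half-width for 30 subjects is 1.96 × √(0.0575/30) = 0.0858, or 8.58 per 100. Under independence it is 5.06 per 100. The stated target is not reproduced. That is a separate matter, but it means that SD 0.8 cannot show which event rates are compatible with the target.

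**Rates at which the target can be met.** With independent Poisson counts the half-width is 1.96 × √(rate/960). Setting it to 0.01 gives rate = 960 × (0.01/1.96)² = 0.025. At 5 per 100 the half-width is 1.41 per 100; at 64 per 100 (the Poisson mean implied by SD 0.8, since 0.8² = 0.64) it is 5.06.

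**LS mean.** In a balanced design under working independence, with time levels shared by both periods, the fitted period LS mean equals the crude period rate × GM/AM, where GM and AM are the geometric and arithmetic means of the event totals per time level.

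**Empty time points.** A week holds 60 × 4 = 240 intervals over both periods, so P(empty) = exp(−240 × rate) and P(any of 8) = 1 − (1 − P(empty))^8. For 32 treatment-number levels, replace 240 by 60 and 8 by 32. The ratio column is simulated GM/AM given that no week is empty.

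| Events per 100 | P(any empty week), 8 weeks | LS mean / crude rate when finite, 8 weeks | P(any empty), 32 levels |
|---|---|---|---|
| 1 | 0.53 | 0.88 | >0.999 |
| 1.5 | 0.20 | 0.89 | >0.999 |
| 2 | 0.06 | 0.90 | >0.999 |
| 2.5 | 0.02 | 0.92 | >0.999 |
| 5 | <0.001 | 0.96 | 0.80 |
| 10 | <0.001 | 0.98 | 0.08 |
| 64 | <0.001 | 0.997 | <0.001 |

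Between-subject variation (gamma frailty, CV 1) changes these little: 0.54 and 0.88 at 1 per 100, 0.03 and 0.92 at 2.5.

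**GEE fits** (60 simulated trials per setting, independence working correlation, robust standard errors). With 32 levels and a true rate of 2 per 100, the median half-width was 0.001 per 100 and the interval covered the true rate in 12% of trials. This is the false precision described above.

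**Subject as a fixed effect, no time term** (20 runs). Median LS mean / crude rate was 0.002, 0.41 and 0.91 at 2, 5 and 10 per 100. Adding 8 weeks gave 0.002, 0.40 and 0.89.

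**Period only, subject as cluster.** The ratio was 1.000 at every rate tried from 1 to 64 per 100, with 93-96% coverage of the true rate.

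**Kt/V week coding.** With class-coded subject, period and week, Weeks 2-9 and 10-19 give 1 + 30 + 2 + 18 = 51 columns with rank 47. Period has 0 degrees of freedom and neither period LS mean is estimable. Weeks 1-8 in both periods give 41 columns with rank 38, 1 degree of freedom for period, and both means estimable.

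**The case against.** The strongest reply is that the failure depends on choices the SAP does not state. That is largely true. An identity link would give arithmetic means. Table 41 uses the time-point column for two halves of a period; coded that way, the LS mean is at most about 3% low from 1 per 100 upward. The probabilities above also assume 30 subjects, while up to 50 may enrol. At 1 per 100 with 50 subjects in both periods, P(any empty week) falls to 1 − (1 − exp(−4))^8 = 14%. The raw mean is also computed directly, so the LS mean supplies the interval and not the only estimate.

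A reader might also object that the only stated variability implies 64 per 100, where the weekly-coded bias is about 0.3%. But there the half-width is about 5 per 100 and the criterion fails anyway. Under independent Poisson counts, the rates that can satisfy the criterion are those at which the model is fragile.

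A reader might infer that the time term is the sole cause. It is not: subject as a fixed effect does the same without it, so removing time alone would not be enough on that reading.

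A reader might also infer that the Kt/V period means cannot be computed. The documents do not support that. The non-overlapping numbering is in notes to the BUN and alarm shells, Tables 33 and 35: "The final table will display all time points (Weeks 2-9 for In-Center and Weeks 10-19 for In-Home". It is not stated as model coding, and it spans ten In-Home weeks for a period of about eight. Protocol Appendix B restarts week numbers in each period, and Tables 8 and 9 presuppose an estimable period effect. The two failures also need opposite codings: the geometric-average result needs shared time points, whereas non-overlapping weeks would leave the safety LS mean non-estimable as well.

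**Conclusion.** The safety point holds, conditionally. It assumes a log link, class-coded time points shared by both periods, and equal weighting of time points in the LS mean. This is the usual reading of SAP 5.2, but the SAP does not spell it out. With 30 subjects and weekly time points at 1-2.5 events per 100, the interval is centred about 12% to 8% too low when it exists, and a non-finite fit has a chance of about 53% falling to 2%. With 32 interval-level time points, failure is almost certain at those rates. With weekly coding the bias is about 2-4% at 5-10 per 100 and under 1% at 64 per 100. No expected rate is given, so none of these can be called the trial's actual error. It still goes beyond missing detail, because the stated model can return a biased or unusable interval for a success criterion at the rates where that criterion is attainable.

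The Kt/V week numbering is a minor clarification and not an established error.

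**What to change.** In SAP 5.2 and Protocol 11.6, compute the primary interval from a Poisson GEE with a log link, treatment period as the only model term and subject only as the repeated cluster, with no subject or time-point class terms. State that the period LS mean is back-transformed to a rate per dialysis interval. In Table 16, print that model-based rate beside its interval. Show any time trend in a separate descriptive table.

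The estimate then breaks down only if a whole period has no event; at 1 per 100 that chance is exp(−9.6), about 0.0001 per period. The simulated check of this model used independence working correlation with robust standard errors, so if AR(1) is kept the SAP should specify robust standard errors.

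In SAP 4.2.1, state that week is numbered 1 to 8 within each treatment period, as in Protocol Appendix B.

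The cost is SAP and protocol wording and a few lines of code. The downside is that the main safety model no longer carries a time effect. Make the change before analysis, because choosing a coding after a failed fit would be data-driven.

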8.7 Laboratory Assessments

Each Subject will be required to provide approximately 120ml or 8 tablespoons of total blood for the duration of the trial to monitor the Subject's blood chemistry. Samples will be collected as outlined in Appendix B.

For weekly draws to calculate the Urea Reduction Ratio (URR) and thereby quantify dialysis treatment adequacy, collect approximately 54-57ml into **Yellow top or serum separator tubes** in increments of 3ml or 0.6 teaspoons for pre and post dialysis treatment BUN.

For pre BUN, prior to connecting to Tablo or administering heparin bolus, fill appropriate tubes according to the standard of care.

For post BUN, pull the sample at the conclusion of therapy by reducing the blood pump speed to 100 ml per minute. Allow one minute to elapse at that blood flow rate, then collect the sample according to the standard of care.

Additionally, at least twice during each treatment period (Treatment Period 1, In-Center and Treatment Period 2, In-Home), collect both chemistry and hematology, and iron indices as specified (see Appendix B for tests and timing).

For chemistry, collect approximately 54-57ml into **Tiger top** or serum separator tubes in increments of 3ml or 0.6 teaspoons, according to the standard of care.

For hematology, collect approximately 12ml in **Lavender top** tubes in increments of 3ml or 0.6 teaspoons according to the standard of care.

During visits when both Chemistry and CBC labs will be drawn, the recommended draw order is **Tiger top** or serum separator **followed** by **Yellow top** or serum separator. All samples will be processed according to reference laboratory requirements. No blood samples will be stored or used for permanent or immortal cell lines.

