9.2.2 Other Adverse Events

The Investigator will monitor the occurrence of adverse events for each Subject during the course of the study. All AEs will be listed on the adverse event case report forms. All pre-existing medical conditions and baseline dialysis stability signs and symptoms will be recorded on baseline case report forms for medical history and signs and symptoms.

Starting with the first treatment during Treatment period 1 with the Tablo[™] Hemodialysis System, any new event/experience that was not present at baseline, or worsening of an event present at baseline, is considered an adverse event. Recorded Adverse Events will include, but are not limited to:

- infections (other than those defined in the Primary Safety Endpoint),
- hypotension,

Note: Unchanged, chronic conditions are not adverse events and should not be recorded on the adverse event page of the CRF.

Note: Laboratory values that are abnormal will not be considered as adverse events unless medical intervention is required. Clinical laboratory data will be monitored and values that are outside of the normal ranges will be separately summarized by time point for each treatment period (In-Center and In-Home). During the In-Center treatment period, summary statistics (mean, standard deviation, median, range, n) on laboratory values collected will be computed on the raw data. During the In-Home treatment period, summary statistics (mean, standard deviation, median, range, n) on laboratory values collected will be computed on the raw data. During the In-Home treatment period, summary statistics (mean, standard deviation, median, range, n) on laboratory values collected will be created for each laboratory values collected will be computed on the raw data. Individual tables will be created for each laboratory panel and quantitative parameter combination. In addition, a summary table will be created for each laboratory panel (hematology and chemistry) to display the number and percentage of subjects who have results that fall out of the normal ranges for each laboratory parameter by time point for each of Treatment Period 1 and 2.

Adverse events will be monitored until they are adequately resolved or explained. Should an adverse event be ongoing at the end of the Subject's last study treatment the medical care plan for the Subject will be described and documented.

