A summary table will be constructed to display the following with respect to all study-emergent AEs:

- Subjects with at least one study-emergent AE
- Maximum severity, per subject
- Highest relationship to device, per subject
- Highest relationship to treatment, per subject
- Subjects with at least one SAE
- Deaths

Laboratory Tests

Clinical laboratory tests will be performed at Baseline and at approximately every four weeks through study completion (with the exception of pre and post BUN, which are captured weekly). For each quantitative laboratory test, summary statistics (mean, standard deviation, median, range, n) on the raw data as well as changes from baseline will be presented by timepoint. If multiple labs were performed at a given timepoint, the lab results from the date the site is basing clinical care from will be used and summarized in the analysis tables. A summary table will be provided to show the results for all lab tests, and additional tables

will be provided to show the results for a subset of the lab tests as well as to show results for selected individual lab tests, as listed in Section 7.0.

A summary table of abnormal lab results will also be provided. All summary statistics (mean, standard deviation, median, range, n) will be computed relative to the lab results that fell outside of specified ranges on the raw data. These ranges will be determined prior to data analysis.

Pre and post BUN summary statistics will be provided in a separate table to show the results by treatment period, time point, and treatment number. Parameters include pre BUN, post BUN, difference in pre and post BUN, and URR, where URR is defined as (pre BUN minus post BUN) divided by (pre BUN).

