Table 24. Summary Table of Hematology - HCT (units)
 Outset Medical - Study No. 2014-01
 Safety Population (N=xxx)

Data Type	Treatment Period ^a				
	Baseline ^b	In-Center		In-Home	
		Treatments 1-16	Treatments 17-32	Treatments 1-16	Treatments 17-32
RAW	xxx	xxx	xxx	xxx	xxx
CFB		xxx	xxx	xxx	xxx
RAW	xxx	xxx	xxx	xxx	xxx
CFB		xxx	xxx	xxx	xxx
RAW	xxx	xxx	xxx	xxx	xxx
CFB		xxx	xxx	xxx	xxx
RAW	xxx	xxx	xxx	xxx	xxx
CFB		xxx	xxx	xxx	xxx

^a All summary data are reported as mean values.

^b Baseline value will be taken as the mean value of all baseline measurements.

STATKING Clinical Services (month day, year)

Source Program: xxxxxxxx.sas

The format of this table will be repeated for each laboratory parameter that will be summarized in individual tables, as listed in Section 7.0.

Table 32. Summary Table of Abnormal Laboratory Values
 Outset Medical - Study No. 2014-01
 Safety Population (N=xxx)

Laboratory Parameter	Data Type	Treatment Period ^a				
		Baseline	In-Center		In-Home	
			Treatments 1-16	Treatments 17-32	Treatments 1-16	Treatments 17-32
Number (%) of Abnormal Lab Values ^b		xxx (xxx%)		xxx (xxx%)		xxx (xxx%)
xxx (units)	RAW	xxx	xxx	xxx	xxx	xxx
	CFB		xxx	xxx	xxx	xxx
xxx (units)	RAW	xxx	xxx	xxx	xxx	xxx
	CFB		xxx	xxx	xxx	xxx
xxx (units)	RAW	xxx	xxx	xxx	xxx	xxx
	CFB		xxx	xxx	xxx	xxx
xxx (units)	RAW	xxx	xxx	xxx	xxx	xxx
	CFB		xxx	xxx	xxx	xxx
xxx (units)	RAW	xxx	xxx	xxx	xxx	xxx
	CFB		xxx	xxx	xxx	xxx

^a All lab-specific summary data are reported as mean values for the subset of results that were abnormal.

^b Denominator is the number of non-missing lab values for all subjects, lab parameters, and time points for the respective treatment period.

STATKING Clinical Services (month day, year)
 Source Program: xxxxxxxx.sas

Table 33. Pre and Post BUN Summary Statistics
 Outset Medical - Study No. 2014-01
 Safety Population (N=xxx)

Treatment Period	Time Point	Treatment Number ^a	Parameter ^b	Mean	Std Dev	n	Min	Max	Median
N/A	Week 1	1	Pre BUN	xxx	xxx	xxx	xxx	xxx	xxx
			Post BUN	xxx	xxx	xxx	xxx	xxx	xxx
			Pre BUN - Post BUN	xxx	xxx	xxx	xxx	xxx	xxx
			URR	xxx	xxx	xxx	xxx	xxx	xxx
In-Center	Week 9	4	Pre BUN	xxx	xxx	xxx	xxx	xxx	xxx
			Post BUN	xxx	xxx	xxx	xxx	xxx	xxx
			Pre BUN - Post BUN	xxx	xxx	xxx	xxx	xxx	xxx
			URR	xxx	xxx	xxx	xxx	xxx	xxx
In-Home	Week 19	4	Pre BUN	xxx	xxx	xxx	xxx	xxx	xxx
			Post BUN	xxx	xxx	xxx	xxx	xxx	xxx
			Pre BUN - Post BUN	xxx	xxx	xxx	xxx	xxx	xxx
			URR	xxx	xxx	xxx	xxx	xxx	xxx

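### No SAP table gives the protocol's number and percentage of subjects out of the normal range per laboratory parameter; Table 32 gives means of abnormal results and a pooled count of values instead

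*SAP*

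**What the plan says.** Protocol 9.2.2 commits to a summary table for each laboratory panel (hematology and chemistry) showing the "number and percentage of subjects who have results that fall out of the normal ranges for each laboratory parameter by time point", for Treatment Periods 1 and 2.

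SAP 5.2, under Laboratory Tests, plans one table of abnormal results. Its statistics (mean, SD, median, range and n) "will be computed relative to the lab results that fell outside of specified ranges on the raw data". On those ranges the SAP says only: "These ranges will be determined prior to data analysis".

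The shell for that table, Table 32 in SAP Appendix B, is narrower than the SAP text. Its first footnote reads "All lab-specific summary data are reported as mean values for the subset of results that were abnormal". Each parameter has one raw cell and one change-from-baseline cell per time window (treatments 1–16 and 17–32 of each period), with no split into low and high. The only count is a row for the number and percentage of abnormal values, entered once each for Baseline, In-Center and In-Home. Its footnote reads "Denominator is the number of non-missing lab values for all subjects, lab parameters, and time points for the respective treatment period".

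**The concern.** The protocol's display answers a simple safety question: on this parameter, at this time, how many of the subjects tested were out of range? The SAP's display changes both the unit (results instead of subjects) and the statistic (a mean of the abnormal results instead of a count and percentage). The mean says how abnormal the abnormal results were, not how common they were.

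Clinical laboratory results are a named secondary safety variable in SAP 5.1. Under Protocol 9.2.2 an abnormal value is not an adverse event unless it needs medical intervention, and Protocol 9.1.3 treats potassium and phosphorus levels as observations. Out-of-range values that need no intervention are therefore absent from the adverse event tables, and the laboratory tables are where their frequency has to be seen. At stake is whether the report can say, parameter by parameter, how many subjects were out of range In-Center and how many In-Home.

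**Working it through.** The plan states no figure to reproduce here. The check compares the texts and then uses arithmetic to show what the Table 32 shell would and would not reveal.

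**1. Protocol against SAP**

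| Feature | Protocol 9.2.2 | SAP 5.2 text | Table 32 shell |
|---|---|---|---|
| Unit | Subjects | Results | Results |
| Statistic | Number and percentage | Mean, SD, median, range, n | Mean only, plus one pooled count row |
| Per parameter | Yes | Yes | Means yes, count no |
| Ranges | Normal ranges | Still to be fixed | Not stated |

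The SAP text and its own shell disagree on which statistics are printed.

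**2. Is the display elsewhere?** SAP Section 7.0 lists Tables 1 to 43. Table 32 is the only abnormal-laboratory table. The shells for Tables 22 to 31 print means of all results. None gives subjects out of range.

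**3. What the pooled count row can show.** Inputs:
- subjects: 30 (SAP 1.3: "a sample size of $n=30$ subjects will be needed for the study");
- draws per period: 2, the minimum in Protocol 8.7 ("at least twice during each treatment period");
- tests: 15 or 16 in the chemistry list of Protocol Appendix B, depending on whether total and direct bilirubin count as one or two, plus 5 in the CBC list, so 20 or 21.

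The denominator with complete data is subjects × draws × tests:
- 30 × 2 × 20 = 1,200;
- 30 × 2 × 21 = 1,260.

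Contribution of one parameter to the pooled percentage:
- Ten subjects (10/30 = 33%) abnormal at both draws give 20 values: 20/1,260 = 1.6% to 20/1,200 = 1.7%.
- All 30 subjects (100%) abnormal at both draws give 60 values: 60/1,260 = 4.8% to 60/1,200 = 5.0%.

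Adding three iron indices once per period raises the larger denominator to 1,260 + 90 = 1,350, and the two contributions become 1.5% and 4.4%. Nothing in the row shows which parameter is responsible.

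**4. What the mean can show.** The values and the range of 3.5 to 5.0 below are assumed for illustration only.

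- *Frequency.* One subject at 6.5 (1/30 = 3.3%) and ten subjects at 6.5 (10/30 = 33%) give the same cell, 6.5.
- *Mixed directions.* Three lows of 2.5 and three highs of 6.5, from six subjects at one time point, give (3 × 2.5 + 3 × 6.5)/6 = 4.5, inside the range. The protocol's display gives 6/30 = 20% of subjects out of range.
- *How special that mix is.* With a share w of lows, the mean is 2.5w + 6.5(1 − w) = 6.5 − 4w. It lies in 3.5 to 5.0 when (6.5 − 5.0)/4 ≤ w ≤ (6.5 − 3.5)/4, that is 37.5% to 75% lows. With lows of 2.8 and highs of 6.2 the interval is 35.3% to 79.4%.
- *Outside that mix.* Two lows and four highs give (2 × 2.5 + 4 × 6.5)/6 = 5.17. One low and five highs give 5.83. Both are out of range.

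**The case against.** The strongest reply is that SAP 5.2 lists more than the mean. A printed range would expose values on both sides at once. A printed n would count abnormal results per parameter. Because SAP 5.2 also selects one laboratory result when several are drawn at a time point, that n would come close to the number of subjects out of range. This stands for the SAP text. It does not stand for the shell, which prints neither, and even the fuller list gives no percentage of subjects tested.

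A second reply is that Protocol 9.2.2 also says, separately, that out-of-range values will be summarized by time point, and Table 32 can be read as doing that. This is fair, but the subject-count table is stated as an additional display and is still missing.

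Three stronger readings are tempting, and the documents do not support them.
- *That dangerous values will be averaged away.* The SAP does not say that highs and lows are pooled; this is inferred from the unsplit cell. A mean inside the range needs a two-sided range and a suitable mix. Out of range is not the same as dangerous, and a table titled as abnormal values would warn its reader. Values needing medical intervention become adverse events under Protocol 9.2.2, and serious adverse events count in the primary safety endpoint.
- *That In-Center and In-Home cannot be compared at all.* The pooled percentage is given for each period, so a crude overall comparison is possible.
- *That the protocol requires separate low and high counts.* It refers only to results out of the normal ranges; a split by direction would go beyond it.

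**Conclusion.** The point holds as a conflict between protocol and SAP in a descriptive secondary safety display. The per-parameter, per-time-point number and percentage of subjects out of the normal range is promised in Protocol 9.2.2 and appears in no SAP table. Table 32 substitutes a mean of abnormal results, which does not measure frequency, and a pooled count of values. In that count, one-third of 30 subjects abnormal on one test at both draws add about 1.6 to 1.7 percentage points. The SAP text and the shell also disagree on the statistics, and the SAP's undetermined ranges are not tied to the protocol's normal ranges.

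The conflict itself rests on the texts alone. The dilution figures assume 30 subjects with complete data, two draws per period and 20 or 21 tests. The in-range mean is a possibility shown with assumed values, not a prediction. The hypothesis tests, the success criteria and the sample size are untouched. It should be corrected before analysis.

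**What to change.** Revise the abnormal-results paragraph of SAP 5.2 and the Table 32 shell together.

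1. For each parameter and time point in each treatment period, report the number and percentage of subjects out of the normal range, as Protocol 9.2.2 states, with subjects tested at that time point as the denominator.
2. As an improvement beyond the protocol text, split these counts into below and above range.
3. Drop the means of abnormal results, or report them separately for low and high results. Make the SAP text and the shell list the same statistics.
4. Reconcile the SAP's ranges with the protocol's normal ranges, and state them or their source in the SAP.

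The cost is one SAP paragraph and one reprogrammed table shell. No new data are needed.
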